footwear). Polar Heart Rate Monitor watches will be swapped via mail or in person (subjects may drop off at CMC VAMC with study staff who will swap and mail new monitors to subjects) monthly based on subject preference. The trainer will view the heart rate files and discuss any need for revising workout schedule or intensity with subjects based on this objective data. Study staff will contact the participants weekly for brief phone counseling and to discuss recent exercise sessions and any need for support. Telephone support has been shown to be an effective method of supporting exercise adherence (86). It is anticipated that these calls will take less than 10 minutes each. During these calls, participants will be asked to report any symptoms or soreness so that the stretching, footwear, and exercise sessions can be modified to ensure injuries are minimized. A phone script template detailing the topics that will be discussed in each call and will be used as a data recording instrument is provided as an appendix.

Exercise setting: The exercise training sessions will take place in the home neighborhoods of the participants. Study staff will help subjects find appropriate local facilities or outdoor routes for the walking intervention. The choice to do the exercise training in the community is based on evidence from the literature that adherence to a home based program is higher than for a facility based program and data from multiple long term weight loss maintenance interventions that indicate that this approach is feasible and sustainable for research subjects (87, 88). The most commonly reported barrier to participation in regular exercise is lack of time (89), and home-based exercise will remove the time that would be spent traveling to and from a facility. The participants recruited into this study may be relatively sedentary. However, we anticipate that they will be able to complete three 30 minute sessions at 40-60% of age predicted maximal heart rate from the first week of training, increasing to the target as advised by study staff based on tolerance.

Assessment of compliance: Compliance with the prescribed exercise regimen will be measured using data from Polar heart rate monitors and subject-completed exercise logs. A reported exercise session in subjects' logs will be judged as completed if the heart rate monitor data supports that the subject achieved 75% or more of the prescribed time in the heart rate range suggested for each individual. The overall percentage of sessions completed will be treated as continuous variable, or, for dichotomous analyses, subjects will be judged as compliant if they completed at least 75% of the prescribed exercise sessions. For subjects taking beta-blockers, heart rate requirements will be decreased by 20% and effort will be prescribed according to Borg RPE as described above. This standard exceeds the ACRM/ACSM recommendations of 150 minutes/week of moderate activity. Subjects will receive weekly phone calls from study personnel to review heart rate records and exercise logs to provide feedback and encouragement to increase or maintain exercise levels.

Assessment of energy expenditure (EE): Energy expenditure throughout the intervention will be estimated using the Flex-HR method with individual calibration from exercise testing data to adjust for the non-linear relationship between HR, VO₂ and energy expenditure at high and low levels of activity(90, 91). The Flex-HR will be considered as the average between the highest resting HR and the lowest recorded exercise HR during exercise testing and combined with estimates of basal metabolic rates to determine total EE according to the method of Spurr(92). Additionally, EE will be estimated at baseline, 8 weeks and 52 weeks in all subjects using accelerometry in the "free-living" condition. Participants will be asked to wear an accelerometer (Actigraph GT3X, FI; Actigraph, Pensacola, FL) that records movement on the vertical and horizontal axis, during waking hours for 7 consecutive days. This instrument is the most widely used objective monitor of physical activity used in research, including use in NHANES (93), which provides population based norms for a broad cross-section of U.S. residents. Participants will be given the accelerometer in person at study visits as described and provided with standardized instructions for use. Accelerometers will be returned by prepaid mailer provided by the study. The accelerometers will be initialized and downloaded using the ActiLife software provided by the manufacturer (ActiGraph LLC). The data will be collected in 10-s epochs. Actilife software will be used to implement quality control procedures, derive wear time, and summarize minute-by-minute data. Non-wear time will be defined as intervals of at least 60 consecutive minutes of 0 cpm, with allowance for up to 2 min of observations of some limited movement (>50 cpm) within these periods. Days with at least 10 h of wear time that did not contain excessively high counts (>20 000 cpm) will be considered valid.

Monitoring of control subjects: All subjects (control and intervention) with abnormal DaT SPECT will be referred to the PADRECC for clinical followup including usual care for monitoring of symptom progression and institution of any necessary symptomatic therapies. Study participation will not limit any aspect of routine clinical care. Importantly, levodopa and other common dopaminergic therapies do not interfere with lofupane binding to dopamine transporters and do not significantly influence DaT SPECT. Enrolled non-intervention subjects will receive similar weekly phone calls from study staff as will intervention subjects. During the weekly phone calls, staff will administer the Parkinson's Disease Questionnaire-8 (96), a short well-validated assessment of parkinsonian symptoms and quality of life that can be completed in only a few minutes. During the baseline visit, at 8 weeks and at the 52 week assessment, study staff will administer the International Physical Activity Questionnaire, a well-characterized self-report instrument that has also been used to measure physical activity in subjects with PD(97, 98), allowing monitoring of any changes in activity over the course of the intervention using paired t-tests.

Study Design:

AIM 1: To test the effect of regular aerobic exercise on motor function in DIP. In this aim, we will test the hypothesis that a short term home exercise regimen will improve motor function in DIP subjects and could be an effective rehabilitation intervention.

Subjects/Procedures: A cohort of DIP subjects with presumed prodromal PD will be defined by a two-tiered screening procedure. First, DIP subjects will undergo olfactory testing administered by trained study personnel. Subjects with hyposmia (defined as scores below the 25th percentile for age and gender using well-established normative data for the UPSIT) on initial olfactory testing will undergo DaT imaging. We will also recruit subjects with a clinical diagnosis of PD by a PADRECC provider. SPECT scans will initially be read as normal, mildly abnormal or clearly abnormal, in accord with current clinical practice, by a nuclear medicine physician blinded to clinical status. High inter-rater agreement (kappa 0.89-0.93) has been reported for clinical reading of DaT(99). All patients with abnormal (mildly or clearly) DaT SPECT will be referred for clinical follow-up in the PADRECC. The combination of DIP, hyposmia and abnormal striatal DaT imaging will be operationally defined as prodromal PD. All subjects with abnormal olfaction and DaT deficit will undergo baseline motor testing (UPDRS motor and instrumented Timed Up and Go) together with safety screening for exercise. If eligible based on safety screening, baseline cardiovascular fitness testing (VO₂max measurement) will be obtained as described above. Subjects will be then be randomized in a 1:1 ratio to a home-based exercise intervention (5 days/week aerobic walking with confirmation by remote activity monitoring) or no intervention. Subjects will receive weekly phone calls from staff to monitor safety and compliance. After 8 weeks, subjects will undergo repeat clinical (UPDRS motor), quantitative (iTUG) and fitness testing (VO₂max) to examine short-term symptomatic effects of exercise. Eight weeks is a common duration for short-term rehabilitation interventions and was recently reported in a Phase I/II trial of aerobic walking in PD(8).

AIM 2: To test whether regular aerobic exercise influences disease progression in prodromal PD. In this aim, we will test the hypothesis that exercise subjects will exhibit slower decline in semi-quantitative striatal DaT SPECT, suggesting a disease-modifying effect of exercise in prodromal PD.

Subjects/Procedures: Subjects will be the same prodromal PD cohort described above in Aim 1. Subjects will continue the exercise intervention (or no intervention) for a total of 52 weeks to examine a potential disease-modifying effect. Subjects will continue to receive weekly phone calls from staff to monitor safety and compliance. At the end of the intervention period, control and exercise subjects will undergo repeat DaT SPECT with quantitation of signal in 6 different striatal regions (right and left caudate, right and left anterior putamen, right and left posterior putamen) and repeat exercise testing. If subjects choose to drop out, we will attempt to obtain the final DaT imaging study as soon as possible after notification of the subject's intent to withdraw if they have completed at least 24 weeks of the intervention.

AIM 3: To characterize the mechanism and biochemical correlates of exercise-induced changes in subjects with prodromal PD. In this aim, we will test the hypothesis that serum biomarkers of exercise effects and PD risk will change in the intervention group compared to no intervention.

Subjects/Procedures: Serum biomarkers associated with PD risk or exercise-induced changes (i.e. BDNF, uric acid and apolipoproteinA1) will be measured at baseline, 8 and 52 weeks as described above. The primary outcome of this aim will be differences in the rate of change between intervention groups as assessed using independent samples t-tests. A secondary outcome will examine the rate of change using linear mixed-effects models controlling for age, gender and other potential confounders. Additionally, relationships of biomarkers to VO2max, UPDRS, quantitative motor and quantitative DaT will be examined using partial correlations controlling for age and gender. An intention-to-treat analysis will be applied primarily but pre-planned secondary analyses will compare only exercise subjects deemed compliant with controls.

A schematic demonstrating the flow of recruitment, assessments and analysis is provided below:

[figure not shown]

Figure 3: Overview of study design

5.1.2. What research methods will be used in the project? *Check all that apply.*

 Surveys/Questionnaires	 Interviews	 Audio Taping
 Behavioral Observations	 Chart Reviews	 Video Taping
 Focus Groups	 Randomization	 Double-Blind

Control Group **Placebo** **Withhold/Delay Treatment**
 Specimen Collection **Deception** **Telephone Survey**
 Other (Describe)

5.1.3. **Provide description of the study population (delineate all categories of subjects – male, female, inpatients, outpatients, providers, family members, employees, etc.). Include anticipated initial enrollment numbers (and number of subjects anticipated to complete all aspects of the protocol).**

Patients aged 40-89 with a clinical diagnosis of DIP will be recruited from the CMC VAMC PADRECC and Behavioral Health Service (BHS) clinics. We will recruit subjects with parkinsonian signs (rest tremor, rigidity, bradykinesia) occurring after the institution of therapy with a antipsychotic medication having known dopamine receptor blocking activity (examples include haloperidol, chlorpromazine, fluphenazine, perphenazine, risperidone, thioridazine, thiothixene, ziprasidone, olanzapine and aripiprazole). Potential subjects with DIP will be pre-screened using a brief (12 item) scratch and sniff smell test with hyposmic subjects invited to learn more about the study (see script). Brief olfactory testing should be completed in 5-10 minutes. We anticipate screening 250 subjects with olfactory testing. Approximately 120 subjects will undergo baseline assessment including DaT-SPECT as described above. Subjects with abnormal DaT-SPECT will be invited to be randomized into the exercise study. In addition to the screening described above, we will invite subjects from [name] CPPF pilot study "Degenerative nigrostriatal dysfunction in drug-induced parkinsonism" PROM#01481 who have abnormal DaT-SPECT to enroll in the present protocol. These subjects will have explicitly agreed to future contact for related studies in the ICF for PROM#01481. We may also invite subjects identified by their PADRECC provider who had DaT-SPECT (with an abnormal result) performed clinically outside of a research protocol within the prior 3 months and agree to be contacted. We will randomize 88 subjects to either exercise intervention or no intervention and anticipate that 70 subjects will complete all aspects of the study. Additionally, letters will be sent to potential participants letting them know that they may be eligible for a study with a brief description of the study and give them a number of they would like to learn more or to request no further contact. 2018 Amendment: We anticipate enrolling 56 additional subjects under the modified inclusion criteria with 48 (24 per group) expected to complete all study activities. This will still allow for meaningful analysis of our primary outcomes according to the sensitivity analysis of sample size from the original protocol (20 per group adequate).

5.1.4. **As applicable, provide rationale and information on any added protections and safeguards for vulnerable populations (children, prisoners, pregnant women, physically or mentally-disabled persons, and economically or educationally disadvantaged persons).**

NA

5.1.5. Does this project target a specific race or ethnic group as participants? **NOT APPLICABLE** If yes, check all that apply.

Race

Ethnicity

- American Indian or Alaska Native
- Asian
- Black or African American
- Native Hawaiian or other Pacific Islander
- White
- Other

- Hispanic or Latino
- Not Hispanic or Latino

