The primary exercise to be performed will be moderate-intensity aerobic walking (60-80% of age adjusted maximum heart rate) for 45 minutes (including 5 minutes each of warm up and cool down), 5 times per week. In individuals for whom heart rate response to exercise is not an accurate indication of intensity, the Borg rated perceived exertion (RPE) will be taught as above and used to monitor intensity. Participants using RPE will be asked to exercise at an intensity level of 12-15 on a scale of 6-20. Overall, this level of exercise exceeds ACSM/ACRM guidelines and has been associated with increases in serum BDNF, a likely marker and/or mediator of the benefits of aerobic exercise. Exercise subjects will also receive a Pedlar® Light Workout Exerciser (Patterson Medical Item #5252). This lightweight pedal exerciser will allow subjects to exercise using their arms or legs in the home when outdoor walking is not feasible (e.g., inclement weather). This model is currently provided to Veterans through our prosthetics department for home exercise. In the event that this model was no longer available through VA, a comparable model available through the prosthetics department would be substituted and an updated IRB amendment would be submitted. The targets for time and heart rate will be the same as those for walking. The Pedlar® will arrive at the subjects' homes fully assembled and at no cost to them. It will be theirs to keep at the end of the study. Subjects will receive training on use of the Pedlar® at their baseline EMU visit. Exercise adherence and intensity will be monitored by subject report and supported by heart rate response from the Polar heart rate monitor. Each participant in the intervention arm will be provided with a Polar heart rate monitor and ongoing support from study staff. Participants will receive instruction in how to use the Polar Heart Rate monitors from the fitness professionals and instructions not to exceed 85% of maximal heart rate during exercise sessions. An exercise professional will instruct participants in the use of the exercise logs and injury prevention (warm-up, cool down, stretching, proper

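### The compliance rule guarantees only about 98 to 127 in-range minutes a week, not the more than 150 the plan claims for it

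*Combined protocol and SAP*

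**What the plan says.** All of the exercise text is in section 5.1.1 of the combined protocol and SAP.

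- **Regimen** (Home exercise, monitoring and promotion of adherence). The exercise is "moderate-intensity aerobic walking (60-80% of age adjusted maximum heart rate"), done for "45 minutes (including 5 minutes each of warm up and cool down), 5 times per week". The same paragraph separately states that this level of exercise is above the guideline level.
- **Completed session** (Assessment of compliance). A logged session counts if the monitor data support that the subject "achieved 75% or more of the prescribed time in the heart rate range suggested for each individual".
- **Compliant subject** (same paragraph). For yes/no analyses, "subjects will be judged as compliant if they completed at least 75% of the prescribed exercise sessions".
- **The claim** (same paragraph, after one sentence on beta-blocker users). "This standard exceeds the ACRM/ACSM recommendations of 150 minutes/week of moderate activity".
- **Starting workload** (Exercise setting). Subjects are anticipated to manage three 30-minute sessions at 40-60% of age-predicted maximal heart rate from week one, "increasing to the target as advised by study staff based on tolerance". No timetable is given.

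Section 9.2 (Aims 1 and 2) and the Aim 3 text in section 5.1.1 make intention-to-treat primary. Each adds a pre-planned secondary comparison of compliant exercise subjects with controls.

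**The concern.** The 150-minute sentence sits in the paragraph that defines compliance, so it reads as a property of the compliance rule. The rule multiplies two 75% thresholds, and a subject who just meets both has done much less than the full prescription. If the claim is carried into a report, the compliant-only results will be attributed to a weekly dose that the rule does not guarantee.

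Two definitions that decide who is compliant are also open. *Prescribed time* may mean the whole 45 minutes or the part outside warm-up and cool-down. The prescribed sessions and range may mean the five-session regimen or the individual's current workload during build-up. Two analysts could classify the same heart-rate file differently, so the compliant population could be settled after the data are seen.

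**Working it through.** **Inputs, all from section 5.1.1:** 45 minutes per session, of which 5 + 5 = 10 are warm-up and cool-down, leaving 35; 5 sessions a week; 75% of time in range per session; 75% of sessions; benchmark 150 minutes a week.

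**Step 1. Reproduce the plan's claim.** For the full prescription, 5 x 45 = 225 and 5 x 35 = 175 minutes a week. Both exceed 150, so the claim is true of the prescription.

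**Step 2. Session threshold alone.** 0.75 x 5 = 3.75 sessions a week on average.
- All 45 minutes counted: 3.75 x 45 = 168.75, above 150.
- Only 35 minutes counted: 3.75 x 35 = 131.25, below 150.

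**Step 3. Both thresholds, which is the rule as written.** Minimum = sessions x 0.75 x minutes x 0.75.

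| Basis | Minutes needed per session | Minimum per week | Share of prescription | Shortfall from 150 |
|---|---|---|---|---|
| 45 minutes count | 0.75 x 45 = 33.75 | 3.75 x 33.75 = 126.6 | 126.6/225 = 56% | 23.4 (16%) |
| 35 minutes count | 0.75 x 35 = 26.25 | 3.75 x 26.25 = 98.4 | 98.4/175 = 56% | 51.6 (34%) |

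The share is 0.75 x 0.75 = 0.5625 on either basis. Dividing 98.4 by 225 would mix the two bases and should not be done.

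**Step 4. Does rounding rescue it?** Requiring 4 whole sessions every week gives 4 x 33.75 = 135 or 4 x 26.25 = 105, still below 150.

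**Step 5. What would make the claim true?** Keeping 75% of time in range, the session threshold would have to be 150/(0.75 x 225) = 88.9% on the 45-minute basis. On the 35-minute basis it would be 150/(0.75 x 175) = 114%, which is impossible.

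**Step 6. How much does the meaning of *prescribed time* matter?** The session cut-off moves from 33.75 to 26.25 minutes. If warm-up and cool-down fall below the range, a cut-off of 33.75 requires 33.75/35 = 96% of the main bout in range. The other reading requires 75% of it.

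**The case against.** **The sentence may refer to the regimen.** The home-exercise paragraph makes the same kind of claim about the regimen, and there it is true. But because that claim is already made there, a second one placed after the thresholds is naturally read as being about them. If the regimen is meant, the text should say so. This part of the objection makes the fault one of wording; it does not remove it.

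**The figures are floors, and total activity can be higher.** Both points are correct. Three-quarters of full 45-minute sessions is 168.75 minutes. But the rule checks only time in range, the benchmark is moderate activity, and 168.75 exceeds it only if warm-up and cool-down count as moderate.

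**A stronger reading on the starting workload.** A reader might infer that someone who never moves beyond the starting workload is classed as compliant on 0.5625 x 90 = 50.6 minutes a week. The documents do not establish this. The starting workload is worded as an expectation, not a prescription, and against the five-session regimen three sessions are 3/5 = 60%, which fails the 75% threshold. The individual range can be explained by age-adjusted maximum heart rate and the beta-blocker adjustment. What stands is that the text does not say which workload is the reference, while it also lets the trainer discuss revising schedule or intensity.

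**A stronger reading on dose measurement.** A reader might infer that compliance is the plan's only check on delivered exercise. It is not. Section 5.1.1 also plans heart-rate-based energy expenditure throughout, accelerometry at baseline, 8 and 52 weeks, an activity questionnaire at those times (described under monitoring of controls), and repeat exercise testing at 8 and 52 weeks. An under-exercised compliant subject could be seen in those data, although none of them defines the flag.

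**Conclusion.** The point holds. As written, the 150-minute claim is wrong for the compliance rule, whose guaranteed minimum is about 98 to 127 in-range minutes a week, or 56% of the prescription on either basis. That is 16% to 34% short of 150. Only the full prescription, at 175 to 225 minutes, reliably exceeds it.

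This rests on applying both thresholds to the five-by-45 regimen, on taking time in range as the plan's measure of moderate activity, and on the plan's own 150-minute benchmark.

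The consequence is limited to the description and reproducibility of the secondary compliant-only comparisons. The primary intention-to-treat analyses, the power calculations and the exercise prescription are unaffected. The correction should be made, but it does not threaten the trial's main conclusions.

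**What to change.** 1. Delete the sentence under Assessment of compliance. Alternatively, restate it so that the 150-minute comparison applies to the full prescription (175 to 225 minutes a week) and the rule is described as guaranteeing at least about 98 or 127 in-range minutes, according to the basis chosen.
2. Before analysis, state which minutes make up *prescribed time*. Either basis can be defended, but one must be fixed.
3. Reconcile the home-exercise, exercise-setting and compliance paragraphs on whether sessions and range are scored against the five-by-45 regimen or the individual's current workload. Say how the existing beta-blocker adjustment enters the scoring.
4. Beside each compliant-only analysis, report delivered in-range minutes per week over weeks 1-8 and 1-52 from the heart-rate files.

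The cost is a wording change and a further summary of heart-rate data already collected. No visit, assessment or change to the exercise prescription is involved. The downside is that the stated minimum dose for a compliant subject becomes less favourable.

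### The accelerometer non-wear rule contradicts itself: it tolerates brief limited movement but bounds that movement from below (above 50 cpm), so wear time can be wrong in either direction

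*Combined protocol and SAP*

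**What the plan says.** All of the relevant text is in Section 5.1.1, under Assessment of energy expenditure.

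- Purpose and timing: "EE will be estimated at baseline, 8 weeks and 52 weeks in all subjects using accelerometry", with the device worn during waking hours for 7 consecutive days.
- Processing: "Actilife software will be used to implement quality control procedures, derive wear time, and summarize minute-by-minute data".
- Non-wear: "Non-wear time will be defined as intervals of at least 60 consecutive minutes of 0 cpm", followed by the allowance "with allowance for up to 2 min of observations of some limited movement (>50 cpm) within these periods".
- Day validity: "Days with at least 10 h of wear time that did not contain excessively high counts (>20 000 cpm) will be considered valid".

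No other part of the document restates or corrects the non-wear rule, and the ActiLife settings are not given beyond these sentences.

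**The concern.** An allowance inside a non-wear definition exists so that a stray low count, such as a knock to a device lying on a table, does not turn an unworn period into wear. That purpose, and the words the plan uses, call for an upper bound on the tolerated counts. The figure in brackets is a lower bound with no upper bound.

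Two consequences follow from the literal text. Minutes of substantial movement may be absorbed into non-wear together with the still minutes around them. Minutes of 1–50 cpm, the ones that best fit a description of limited movement, are neither zero nor inside the allowance, so they break the interval.

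Wear time, the classification of days against the 10-hour criterion, and the energy-expenditure estimates built on the valid days are at stake.

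**Working it through.** The plan states no figure that depends on this rule, so there is nothing to reproduce. The check is to apply the rule as written, and again with the inequality reversed, to constructed minute-by-minute sequences. The sequences are assumptions chosen to show how the rule behaves. They are not trial data.

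**Inputs from Section 5.1.1:** minimum interval 60 min; at most 2 tolerated minutes; tolerated if above 50 cpm (literal); a valid day needs at least 10 h = 600 min of wear.

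**Assumptions:** a non-wear interval starts and ends on a zero minute; walking is set at 3000 cpm; other wear is set at 300 cpm. The reversed rule tolerates non-zero counts below 50 cpm. Using 50 or below gave identical results.

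**Step 1: minutes scored as non-wear**

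| Sequence | True state | Length | Literal (>50) | Reversed (<50) |
|---|---|---|---|---|
| A: 30 min at 0, 2 min at 3000 cpm, 30 min at 0 | worn | 62 | 62 | 0 |
| B: 45 min at 0, 1 min at 10 cpm, 45 min at 0 | off | 91 | 0 | 91 |
| C: 120 min at 0 except two separate minutes at 20 cpm (zero runs of 40, 40 and 38 min) | off | 120 | 0 | 120 |

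A gives the same result if the two minutes are at 19 999 cpm. The 20 000 cpm limit decides whether a day is valid and does not cap the tolerated minutes. Each sequence holds at least 60 zero minutes (A: 60; B: 90; C: 118), so the results do not depend on whether the tolerated minutes count towards the 60.

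B and C fail under the literal rule because every run of zeros is shorter than 60 min once the low count has broken it. A zero run of 60 min or more beside a stray count would still be scored as non-wear.

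**Step 2: day validity**

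Wear = other wear + sequence length − minutes of the sequence scored as non-wear. The day is valid if wear ≥ 600 min. Take 560 min of other wear.

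- With A, literal: 560 + 62 − 62 = 560, invalid. Reversed: 560 + 62 − 0 = 622, valid.
- With B, literal: 560 + 91 − 0 = 651, valid. Reversed: 560 + 91 − 91 = 560, invalid.

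The literal rule therefore rejects a properly worn day in one case and accepts an under-worn day in the other. The 560 min was chosen near the threshold to show that the decision can flip. A day well clear of 600 min would keep its status, although its wear time would still be wrong.

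**Step 3: limit on lost activity**

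The allowance covers at most 2 min per interval, so a third minute above 50 cpm ends it. A 45-minute exercise session cannot be absorbed. The larger loss in A is the 60 still minutes of wear, not the 2 active ones.

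**The case against.** The strongest reply is that this is probably a typing slip in the description of a supporting measure, and that the software does the scoring. Much of that stands.

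- **Role of the measure.** A reader might infer that accelerometry is the trial's objective check on whether controls took up exercise. The documents do not give it that role. Section 5.1.1 uses it to estimate energy expenditure, in addition to the heart-rate method. Compliance is judged from heart-rate monitors and exercise logs, and change in activity under Monitoring of control subjects is assigned to a questionnaire. Section 9 names no accelerometry endpoint, test or power calculation.
- **Bias between arms.** A reader might also infer that short bouts in sedentary hours are commoner in controls, so that the error favours one arm. Section 5.1.1 says only that participants in general may be relatively sedentary. Nothing supports a difference by arm.
- **Opposing errors.** Pattern A removes wear time and pattern B adds it. For A to occur, every minute of the hour outside the tolerated two must be exactly zero. One low-count minute can break the interval, so the second defect partly shields worn time from the first.
- **Loss of a day.** The plan sets no minimum number of valid days out of 7, so it defines no consequence for losing one.
- **Actual scoring.** It is unknown whether any file has been or will be scored by the literal sentence.

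These points limit the size of the problem but do not remove it. The next sentence uses the same symbol in its ordinary sense for excessively high counts, so it cannot be read here as meaning up to 50. The sentence is also the only specification in the documents from which staff could configure the software or an analyst could reproduce wear time. If ActiLife is set differently, the protocol misdescribes the method.

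**Conclusion.** The rule is wrong as written, at low severity. The verbal description and the threshold in one sentence cannot both hold. Followed literally, the rule can misstate wear time in either direction (62 min too little or 91 min too much in the examples) and can reverse the 10-hour decision for days near that limit.

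The consequence stops at the accelerometry-based energy-expenditure estimates. The primary outcomes of the three aims (UPDRS motor score, putamen DaT signal, serum biomarkers) and the Section 9 sample-size figures do not use this rule.

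It would go too far to say that genuine activity is being deleted from the trial data: the documents do not show which setting was applied. The net direction and size of the error across participants, and any difference between arms, cannot be determined from the documents. The numerical results rest on the constructed sequences, and the conclusion that the sentence contradicts itself rests on the text alone.

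**What to change.** Restate the allowance as an upper bound that agrees with the verbal description, for example non-zero counts up to 50 cpm for no more than 2 minutes. The documents do not reveal the intended bound, so the investigators should confirm it. Strictly below 50 and 50 or below gave the same results in the check above. Then confirm that the ActiLife wear-time setting matches the corrected sentence and record that setting. Rescore stored files only if they were processed with the literal rule.

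The cost is a one-symbol protocol correction, a settings check and, if needed, a re-run of stored files through the same software. No new data collection and no change to the sample size or the primary analyses is required.
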